Wet-to-dry vs Petrolatum & Non-stick Dressings After Hidradenitis Suppurativa Surgery

 NCT number
 NCT05194969

 Document Date
 8/1/2024

PROTOCOL: INTERVENTIONAL STUDY

Complete Title: Comparison of Wet-to-dry vs Petrolatum and Non-stick Dressing for Second Intention Healing Following Hidradenitis Suppurativa Surgery

Short Title: Wet-to-dry vs Petrolatum & Non-stick Dressings After Hidradenitis Suppurativa Surgery

Drug or Device Name(s):

FDA IND/IDE (if applicable):

Sponsor: University of North Carolina, Chapel Hill

Protocol Date: 8/1/2024

Study Principal Investigator [name] UNC School of Medicine Department of Dermatology [name] [contact] email: [contact]

ABBRE	VIATIONS AND DEFINITIONS OF TERMS	
PROTO	DCOL SYNOPSIS	4
васко	GROUND AND RATIONALE	7
1	STUDY OBJECTIVES	9
2	INVESTIGATIONAL PLAN	
3	STUDY PROCEDURES	
4	STUDY EVALUATIONS AND MEASUREMENTS	
5	STATISTICAL CONSIDERATIONS	
6	STUDY INTERVENTION (DEVICE, DRUG, OR OTHER INTERVENTION)	
7	STUDY INTERVENTION ADMINISTRATION (IF APPLICABLE)	
8	SAFETY MANAGEMENT	
9	DATA COLLECTION AND MANAGEMENT	
10	RECRUITMENT STRATEGY	
11	CONSENT PROCESS	
12	PLANS FOR PUBLICATION	
13	REFERENCES	
APPEN	IDIX	

Abbreviations and Definitions of Terms

Abbreviation	Definition
HS	Hidradenitis Suppurativa
MID	Minimal important difference
NRS	Numeric Pain Rating Scale
PUSH	Pressure Ulcer Scale for Healing
PWAT	Photographic Wound Assessment Tool

PROTOCOL SYNOPSIS

Study Title	
Funder	UNC Department of Dermatology
Clinical Phase	NA
Study Rationale	Hidradenitis suppurativa (HS) is a chronic, severe, inflammatory skin condition characterized by recurring abscesses, nodules, and tunneling sinuses in intertriginous locations such as the groin, buttocks, and axillae. While many patients are managed with medications and lifestyle modifications alone, a subset of HS patients benefit from surgical intervention. Proper wound care following HS surgery is paramount, as facilitating proper healing and minimizing infection can prevent post-operative complications, morbidity and the need for future procedures. This study hopes to answer the question of whether wet-to-dry dressings should be standard of care or whether an alternate form of wound dressings, such as petrolatum with non-stick bandaging, is at least equitable if not superior in effect with fewer drawbacks.
Study Objective(s)	Primary Objectives: - Characterize and compare the 2 regimens via patient-

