	 Characterize and compare the two bandaging regimens in terms of wound healing after surgical deroofing and excisional procedures using the validated PUSH tool

 Characterize and compare the 2 bandaging regimens in terms of pain with dressing changes, as measured by the NRS, after surgical deroofing procedures

Test Article(s)	NA
(If Applicable)	
Study Design	Interventional Study Model: Parallel Assignment
	 This study is a randomized, blinded trial of two postoperative bandaging techniques after HS surgery: wetto-dry dressings vs. petrolatum with non-stick bandaging. Patients will be followed for a minimum of 6 weeks postoperatively with surveys to be completed at home, including a wound photograph, at weeks 1, 2, 4, and 6 weeks postoperatively. If wounds have not healed by week 6, then final healing may be tracked up to 12 weeks to monitor for complications.
	Number of Arms: 2
	Masking: Triple (Care Provider, Investigator, Outcomes Assessor)
	 Following the surgical procedure, the principal investigator (PI) exits the exam room. The PI is not present for bandaging administration and training and thus is blinded to the wound dressing technique. The patient is not blinded as bandaging will be administered at home.
	Allocation: Randomized
	Enrollment: 74
Subject Population	Accepts Healthy Volunteers: No
key criteria for Inclusion	Inclusion Criteria:
and Exclusion:	 Male & females ≥ 16 years of age
	 Patient must have undergone a standard-of-care surgical procedure for HS with planned secondary intention healing of the wound.
	 Must be able to provide adequate informed consent for themselves
	 Must be capable of performing either of the recommended wound care regimens on their own or have someone available to consistently assist with wound care.
	Exclusion Criteria:
	 Patients with surgically closed wounds (sutures, staples)
	 Patients with preference for specific types of bandaging protocols
	 Patients that have not been able to tolerate either wet-to- dry or petrolatum and non-stick bandages in the past

Number Of Subjects	74
Study Duration	Each subject's participation will last at least 6 weeks. Official Dates: April 25 th , 2022 – October 30 th , 2023 (18 months)

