Study Phases Screening Study Treatment Follow-Up Efficacy Evaluations	Study Phases: Phase 1 (Day 0): Screening and Enrollment Phase 2 (Weeks 1–Wound closure): survey completion and wound monitoring Phase 3: Data Analysis Primary efficacy evaluation will be completed using the validated PUSH tool, NRS tool, and Wound QOL survey.
Safety Evaluations	Monitoring for signs of wound infection will be included on regularly scheduled patient surveys. If pain scores become worse following bandaging within one of the wound dressing groups during periodic data reviews, then we may need to stop the study early if this becomes significant. Subjects will have the ability to contact us with any concerns and should other unanticipated adverse events be reported we will track them and address any serious adverse events or trends.
Statistical And Analytic Plan	The general goal is to demonstrate non-inferiority between the two bandaging types. The PUSH tool is the primary endpoint utilized to power for non-inferiority between the two wound bandaging techniques. There is no a-priori rationale for any exact non- inferiority margin. Instead, it is estimated that the expected half- width of a 97.5% confidence interval (i.e., the lower extension of a one-sided, Bonferroni-adjusted 98.75% CI) will be 0.61 SDs. Put differently, there would be 80% power to establish that the non- stick dressing is not 0.84 SDs worse than the wet to dry dressing. Utilizing the sample size of 74 patients calculated using the non- inferiority analysis for the PUSH tool actually provides the study sample size necessary to reliably identify a meaningful difference between the other two primary endpoints, the NRS tool and Wound QOL survey. Primary outcome measures will be reported as means and full ranges.
DATA AND SAFETY Monitoring Plan	We will be compiling and monitoring data on responses on an ongoing basis and reviewing every 2-3 weeks. If one group is demonstrating significantly worse outcomes before the planned end of the enrollment period, we will end the study early and report the results available at that time. All patient data collected in this study will be stored within the secure research software RedCap. Data access will be restricted to the research fellow as the primary data input source. Downloaded

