1.4 Primary Objectives

Primary Outcome Measures:

- 1. Change in Wound QOL Survey Score Over Time
 - a. A validated Wound Quality of Life (QOL) Survey will be administered that focuses on patient-reported outcomes of level of wound pain, pain with dressing changes (application and removal), satisfaction with the bandaging, and ease of application of the bandaging, all

17 elements on a 0-4 scale. Total score ranges from 0 to 4 with higher scores indicating a worse outcome.

- Time Frame: Administered at 1, 2, 4 and 6 weeks post-surgery
- 2. Change in PUSH Score Over Time
 - a. The pressure ulcer scale for healing (PUSH) tool is a validated means of measuring wound healing over time, specifically wounds that heal via secondary intent, by taking into account things like wound size and wound exudate, among others. Scores range from 0-17 with higher scores indicating inferior wound healing.
 - Time Frame: Completed at 1, 2, 4 and 6 weeks post-surgery utilizing images submitted by patients
- 3. Change in Pain with Dressing Changes
 - a. The numeric rating scale (NRS) will be used, where patients will be asked to rate pain with dressing changes and general pain on a scale from 0-10 with higher scores indicating worse pain. This information will be collected in the patient survey that is sent post-operatively.
 - Time Frame: Collected at 1, 2, 4 and 6 weeks post-surgery

Secondary Objective

The PWAT will be an important secondary endpoint for evaluation and comparison with the primary endpoints. Other patient-reported outcomes including interference with daily activities/exercise, assistance needed with bandaging changes, bandage change difficulty, and likelihood to use this bandage type in the future will be assessed. Additionally, patient-reported wound healing will be recorded. This will include questions such as "To what degree is the wound healed?" with answers on a 10-point scale ranging from "completely healed, somewhat healed, not healed." Number of days to wound healing/resolution will be asked on all surveys 4 weeks and later. Patients will also be asked whether or not they believe their wound is showing signs of infection.

2 INVESTIGATIONAL PLAN (brief overview)

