2.3 Study Duration, Enrollment and Number of Subjects

Duration: primary and secondary outcome data will be recorded for up to 6 weeks, and if wounds are not healed by week 6, then subjects may be followed out to 12 weeks for safety.

Planned enrollment: minimum 72, maximum 100. Actual: 74

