The minimal important difference (MID) in Wound-QoL-17 overall score was determined in a German sample of 227 patients with chronic wounds and was found to be approximately 0.5 [4]. This means that a decrease of the Wound-QoL-17 total score of 0.50 or more in a group of patients can be assumed to indicate patient-relevant change. The global score ranges from 0 (= no impairment) to 4 (= maximum impairment). Preliminary statistical analysis indicated that we would need only 3 patients in each study arm to detect this difference. As a result, the study sample size necessary to meet this number to achieve 80% power is far exceeded by the 74 patients needed to detect non-inferiority via the PUSH tool (see Aim 3). We will report means and full ranges for Wound-QOL values in each group across relevant time points.

Aim 3. Characterize and compare the two bandaging regimens in terms of wound healing after surgical deroofing and excisional procedures using the validated PUSH and PWAT tools

Hypotheses for Aim 3: Wound healing in the petrolatum and non-stick bandaging group will be noninferior compared to the wet-to-dry group

The pressure ulcer scale for healing (PUSH) tool is a well-validated and accurate measure of healing for chronic wounds that heal by secondary intention. However, it has not been used frequently by the principal investigator as a measure of wound healing. Given our unfamiliarity in the clinical variance of PUSH scores between patients, we plan to power for non-inferiority between the two wound bandaging techniques in terms of wound healing as opposed to superiority of one bandaging type over the other. We don't have an a-priori rationale for any exact non-inferiority margin. Instead, we estimate that the expected half-width of a 97.5% confidence interval (i.e., the lower extension of a one-sided, Bonferroniadjusted 98.75% CI) will be 0.61 SDs. Put differently, we would have 80% power to establish that the non-stick dressing is not 0.84 SDs worse than the wet to dry dressing.

The photographic wound assessment tool (PWAT) is not a primary endpoint for which the study is powered, but it will still be completed and analyzed as a secondary outcome of interest and reported as means and full ranges.

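### PUSH non-inferiority is planned with no adopted margin and no deciding visit or contrast, so the plan as written cannot give an interpretable non-inferiority verdict

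*Combined protocol and SAP*

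**What the plan says.** The synopsis (Statistical And Analytic Plan) states: "The general goal is to demonstrate non-inferiority between the two bandaging types". It names PUSH as the endpoint used to power for this. Aim 3, under Statistical Considerations, hypothesises that healing with petrolatum and non-stick gauze will be non-inferior to wet-to-dry.

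On the margin, the efficacy paragraph of Statistical Considerations and Aim 3 both say "We don't have an a-priori rationale for any exact non-inferiority margin", and the synopsis says the same in near-identical words. In place of a margin, all three give an expected 97.5% confidence interval half-width of 0.61 SD (equivalently a one-sided 98.75% limit). They restate this as 80% power to exclude a deficit of 0.84 SD. Aim 3 adds that the investigators are unfamiliar with how PUSH varies between patients. No PUSH SD appears anywhere.

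On the endpoint, Section 1.4 (Primary Objectives) defines it as change in PUSH over time: "Completed at 1, 2, 4 and 6 weeks post-surgery utilizing images submitted by patients". The scale is described as "Scores range from 0-17 with higher scores indicating inferior wound healing". No visit, summary contrast or model is named as deciding.

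On reporting, the synopsis says "Primary outcome measures will be reported as means and full ranges".

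On timing, the title page reads "Protocol Date: 8/1/2024", the synopsis gives a study end of October 30, 2023, and Section 2.3 records "Planned enrollment: minimum 72, maximum 100. Actual: 74".

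**The concern.** A non-inferiority conclusion is defined by its margin and by the contrast to which the margin applies. Here the confidence level and the direction of harm are fixed, but the threshold and the contrast are not. The planned output does not help: a mean and a full range give no confidence interval, so a reader could not apply a margin of their own to the published figures.

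PUSH is one of three primary endpoints, and the stated purpose is to judge whether wet-to-dry should remain standard of care. A claim that healing is no worse would carry much of that argument. Under this plan the same data could support or fail to support it, depending on choices the document leaves open.

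**Working it through.** **Inputs from the documents:** one-sided 0.0125 for PUSH (97.5% two-sided); 28 evaluable per arm (the pain calculation in Statistical Considerations); stated half-width 0.61 SD; stated 0.84 SD at 80% power; four PUSH visits.

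**Assumptions, not in the documents:** alternative margins of 0.50 and 0.70 SD; a true deficit of 0.50 SD; equal deficits at all visits; between-visit correlation of 0.3 to 0.9; PUSH SD of 2 to 4 points. Results are in SD units, with the observed SD taken as 1 in steps 1 and 2.

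**1. The plan's own figures.** Half-width = t(0.9875, 2n−2) × √(2/n).
- n = 28: 2.306 × 0.2673 = 0.616
- n = 29: 2.303 × 0.2626 = 0.605

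Power to exclude 0.84 SD with no true difference (noncentral t) is 79.6% at 28 per arm and 81.2% at 29. Both stated figures reproduce, so there is no arithmetic error. The check also shows what 0.84 is: the value that this number of completers delivers.

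**2. The verdict depends on the margin (28 per arm).**
- Observed deficit 0.20: upper limit 0.20 + 0.616 = 0.816. This passes at 0.84 and fails at 0.50.
- Largest observed deficit that passes at 0.84: 0.84 − 0.616 = 0.224.
- At 0.50: 0.50 − 0.616 = −0.116, so non-stick would have to be observed at least 0.12 SD better.

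**3. Power with no true difference (28 per arm).** 79.6% at 0.84 SD, 62.4% at 0.70 SD, 33.9% at 0.50 SD.

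**4. Choice of visit, if 0.84 SD were used as the margin.** Simulated trials, 28 per arm, exchangeable correlation, a claim made if any of the four visits passes:

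| True deficit | One pre-named visit | Any of four, correlation 0.9 | 0.7 | 0.5 | 0.3 |
|---|---|---|---|---|---|
| 0.84 SD | 1.25% | about 2.5% | 3.5% | 4.1% | about 4.6% |
| 0.50 SD | 16% | about 24% | 32% | 38% | 43% |

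**5. Size in PUSH points.** 0.84 × 2 = 1.7 and 0.84 × 4 = 3.4 points on the 0 to 17 scale. The documents cannot narrow this range.

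**6. Basis of 74 (minor and separate).** The opening of Statistical Considerations says the study is powered on pain and quality of life. It builds 74 from pain: 28 per arm, 2 more for covariates, 20% dropout. (56 + 2)/0.8 = 72.5, or 60/0.8 = 75 if the 2 are per arm. The synopsis and Aims 1 and 2 attribute 74 to PUSH. That route also works: 29 per arm for 0.84 SD, 29/0.8 = 36.25, so 37 per arm and 74 in total. The documents do not settle which came first. For pain, 1.3/1.4 = 0.93 SD needs 20 per arm at two-sided 0.05, 24 at 0.025 and 28 at 0.0125; the alpha is not stated. If 28 stands, Aim 1 cannot say that the PUSH requirement greatly surpasses the pain requirement, because 28 and 29 are practically equal.

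**The case against.** **The 0.84 SD is an implied margin.** This is the most natural defence. But the plan offers the figure in place of a margin, as another way of stating the expected interval width, straight after disclaiming any rationale for one. It has no clinical justification and no value in PUSH points. Even if it were accepted, the visit would stay open.

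**The plan is already close to a precision statement.** Largely true, and it is why the repair is cheap. What does not fit is the stated goal of demonstrating non-inferiority and the Aim 3 hypothesis.

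**Change over time need not mean four separate tests.** Fair. One longitudinal contrast could serve, but none is named, so the point stands for the contrast as it does for the visit.

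**The any-visit rates stack assumptions.** They do, and no document gives the true deficit, its constancy across visits or the correlation. At a correlation of 0.9 the inflation is modest. Covariate adjustment would also raise power: if 30% of variance were explained (assumed), power at 0.50 SD would be about 48%, not 34%. Neither changes the absence of a rule.

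**The dates suggest that the margin or visit was chosen after the data.** A reader might infer this, and the documents do not support it. The title page dates this version of the document, not the PUSH text, and the sample-size wording is prospective. The principal investigator scores wounds only at study conclusion (Section 4) and has no patient data until then (synopsis; Section 8). On the other side, Section 8 has responses reviewed every 2 to 3 weeks, and whether anyone saw PUSH by arm is not stated. The dates show only that any margin set now would come after the stated study end.

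**Conclusion.** The point holds and should be fixed before PUSH results are reported. The plan aims at a non-inferiority verdict on a primary endpoint with no margin, no deciding visit or contrast, and no reported interval, so it cannot yield an interpretable one. Nothing in it prevents those choices from being made after results are known; that they were so made is not shown.

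That the outcome can turn on the margin follows from the plan's own numbers plus one assumed alternative: the 0.20 SD example passes at 0.84 and fails at 0.50. Power of 80%, 62% and 34% across 0.84, 0.70 and 0.50 SD rests on 28 completers per arm, an unadjusted comparison and no true difference. The any-visit rates (about 2.5% to 4.6% against 1.25%, and about 24% to 43% against 16%) are conditional on 0.84 SD being used, free choice of visit, equal deficits and the assumed correlations.

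The conflict over the basis of 74 is a wording matter. It does not show that 74 is the wrong number, since both routes lead to about that figure.

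**What to change.** 1. Withdraw non-inferiority as a conclusion for PUSH in the synopsis and in Aim 3. Relabel the 0.61 and 0.84 SD sentences in the synopsis, the efficacy paragraph and Aim 3 as expected precision.
2. Add to the planned summaries the PUSH difference (non-stick minus wet-to-dry), adjusted for wound size and location, with its 97.5% confidence interval at weeks 1, 2, 4 and 6, as estimation. Week 6, the last scheduled primary-outcome visit, can lead the presentation. Alternatively, one longitudinal model can supply all four contrasts, which fits an endpoint defined as change over time. Showing all four keeps the choice of visit from selecting the result.
3. Label this as a change made after the stated study end.
4. Keep a non-inferiority verdict only if the sponsor can document that a margin and a contrast were fixed before arm-level outcomes were seen.
5. Separately, reconcile the accounts of where 74 comes from and state the alpha behind 28 per arm for pain. If 28 stands, remove the Aim 1 statement that the PUSH requirement far surpasses the pain requirement.

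The cost is wording and one interval per visit, with no extra patients or data. The downside is a weaker stated claim for PUSH: an estimate with its uncertainty in place of a verdict.

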5 STUDY INTERVENTION (DEVICE, DRUG, OR OTHER INTERVENTION)

- Description

Bandage: Petrolatum with Non-Stick Gauze

Petrolatum is a petroleum-based bioinert ointment that is non-irritating to the skin [8]. The petrolatum often feels soothing when applied and seems to minimize wound discomfort [2]. After placement of petrolatum, the wound is covered with nonadherent gauze and tape or another bordered dressing. This wound bandaging technique can be placed over the wound once or twice daily to maintain a moist wound base.

- Receipt/Storage

Petrolatum can be safely stored on the shelf at home.

- Treatment compliance and Adherence

Apply once to twice daily to the wound base. There are no other strict adherence requirements.

- Drug Return/Destruction

Petrolatum can be safely disposed of in normal trash receptacles.

6 STUDY INTERVENTION ADMINISTRATION

- Randomization procedures

A stratified block randomization will take place after the principal investigator has left the surgical room following surgery. Randomization will be performed by the research fellow. Each participant is assigned to a particular stratum based on wound size and location, two important covariates to control for in statistical analysis given these variables can impact the Wound QOL survey and other results significantly. After strata assignment, randomization is completed via a RedCap algorithm. A detailed outline of the randomization process and groups can be found in **Figure 1**.

- Blinding procedures

Following the surgical procedure, the principal investigator will exit the exam room. The principal investigator will thus be blinded to the wound dressing technique as he will not be present for bandaging administration, but the patient will not be blinded as they themselves will be administering the bandaging at home.

- Unblinding procedures

If at any point unblinding occurs, the involved patient will be notified that their further participation in the study is voluntary but their patient data can no longer be used for analysis. There is no penalty or direct harm anticipated to the patient because of unblinding. They can continue to bandage their wound as assigned during randomization or alternatively if desired.

- Premature Study Closure

If any of the groups are showing significantly worse outcomes with regard to changes in pain or days to surgical wound resolution before the end of the recruitment period, the study will be ended prematurely.

- Subject Withdrawal

If a subject fails to complete a their one-week postoperative survey or are unable to complete the assigned wound care for a full week, they will be withdrawn from the study. All subjects will have the option to withdraw from the study at any time that they wish.

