1.3 Non-Clinical and Clinical Study Findings

Potential Benefits

There is potential that patients who participate in this research trial will receive additional monitoring compared to patients who do not (as they are receiving follow up surveys), which could help with identifying infection sooner. Analyzing the efficacy of petrolatum with non-stick bandaging at resolving HS postoperative wounds and decreasing pain could help guide dermatologists' treatment of HS and

provide better outcomes for patients in the future, including those in this study that might pursue additional procedures in the future.

Risks

Risks of participation include distress in anticipation of post-operative wound management, pain and discomfort following the procedure and with dressing changes, and infection. However, these risks accompany normal clinical unroofing procedures. There is always a risk of confidentiality breaches, but we will be mindful and attempt to minimize this risk. Normal clinic protocol for post-operative pain management will be followed, which includes opioid and non-opioid analgesics depending on provider and patient preferences and needs. Pain with dressing changes can occur, especially with wet-to-dry dressings. Patients will be informed of this risk during their dressing change postoperatively and during their bandage training session with the nurse. Patients will be instructed to contact the clinic in the event that dressing changes are too painful so that additional pharmacotherapy can be prescribed and other wound management strategies discussed. Patients will be made aware of this risk so that they can opt out of the bandaging protocol if needed.

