2.1 Study Design

Type of design: Randomized Controlled Trial

This will be a randomized, blinded trial of two postoperative bandaging techniques: wet-to-dry dressings vs. petrolatum with non-stick bandaging (see **Table 1).** Primary outcomes will be tracked using the PWAT, PUSH tool, and Wound QOL Survey (described below). Screening will be performed during regularly scheduled clinic visits with the principal investigator. Informed consent will be signed by the subject. A physical exam will be performed to assure that HS lesions suitable for surgical deroofing are present. Once subjects are deemed appropriate for the study, on the day of surgery the surgical sites will be marked with a skin marker and documented by body location. The surgical deroofing or excision procedure will then be performed by the principal investigator.

Study Phases are as follows:

Phase 1 (Day 0): Screening and Enrollment – patient's surgical date

Phase 2 (Weeks 1–Wound closure): patient survey completion and wound monitoring

Phase 3: Data Analysis

On the day of enrollment (patient's surgical date), patient age, sex, race, smoking history, and immunomodulatory medication use will be recorded. Assessment of wound size will also be measured by the PI on the day of surgery. The surgical procedure will be completed as it normally wound if the patient were outside the study. After the PI leaves the room, the patient is randomized to their treatment group and given their wound bandaging supplies and detailed instructions regarding the study protocol.

Patients will be instructed to expect receipt of a virtual RedCap questionnaire via electronic mail 1week post operatively and 2-weeks postoperatively. Questionnaires will continue to be sent every 2 weeks until the wound has fully closed. Disposable rulers will be provided that will be placed beside the wound for scale and patients will be instructed how to measure their wounds. The photos will be depersonalized and examined by the PI. Objective wound assessment will be completed using two standardized assessment tools. Wound assessment will be completed with the validated photographic wound assessment (PWAT) tool and the photographs will also be used to score and track wounds using the validated pressure ulcer scale for healing (PUSH) tool.

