3.6 Screen failure procedures

If a patient does not meet inclusion criteria at enrollment, normal clinical care will resume with no detriment to the patient.

4 STUDY EVALUATIONS AND MEASUREMENTS (how measurements will be made)

- List variables that will be abstracted from medical charts

Page **12** of **20**

Baseline demographics including age, sex, race, BMI, smoking history, among others will be recorded from the medical chart and verified with the patient on the day of enrollment.

- Describe baseline evaluation

Baseline evaluation will include identifying surgical site, evaluating if surgical site is optimal for study inclusion, assessment of patient's overall general health,

- Describe how measurements will be taken.

Patient's upload a photo of their wound with each online survey they complete, as well answers to questions such as pain with wound dressing changes on a scale 1-10. Wound measurements and wound characterization for the primary and secondary endpoints will then be completed at the conclusion of the study by the PI. Other questions and data will be inputted by patients directly on the survey for future statistical evaluation.

- Describe rating scales, tests, psychological tools, laboratory evaluations, etc.

The previously-described PUSH, Wound QOL, and NRS primary endpoints will all be recorded and extrapolated from the online surveys submitted by patients at scheduled intervals.

STATISTICAL CONSIDERATIONS

Our study is powered to detect an effect on our primary endpoints, pain and quality of life. Although we will use the Wound Quality of Life (QoL) survey for our main analysis, as it is more comprehensive and we think readers will find it more persuasive, we don't have direct data on what to expect. Rather, we do have a strong sense, from clinical experience, of what will happen with pain. Using the 0-10 numerical pain scale, we believe the non-stick dressing will reduce pain ratings by 1.3 points at the two-week checkup and estimate the historical SD at that visit is 1.4 units, implying a .93 SD reduction. We calculate we will need 28 patients per arm to achieve 80% power. We add 2 more to account for two planned covariates (pelvic area vs armpit, and initial wound size). Since we expect approximately 20% dropout, we will plan to recruit approximately 74 patients.

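### The unblinding rule discards patient-reported pain and quality-of-life data that PI blinding cannot affect, and the loss can depend on outcome and arm

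*Combined protocol and SAP*

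**What the plan says.** Section 6, Unblinding procedures, provides that if unblinding happens at any time, "the involved patient will be notified that their further participation in the study is voluntary". The notice to the patient has a second part, which is the rule at issue here: "their patient data can no longer be used for analysis". It draws no distinction by endpoint, by visit, or between data given before and after the event. No other section keeps these patients in an analysis. The same paragraph lets an unblinded patient continue the assigned dressing or use another.

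On who is blinded, the synopsis masks the care provider, investigator and outcomes assessor. Section 6, Blinding procedures, says "the patient will not be blinded as they themselves will be administering the bandaging at home".

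On who scores what, Section 2.1 says "The photos will be depersonalized and examined by the PI", and Section 4 says "Wound measurements and wound characterization for the primary and secondary endpoints will then be completed at the conclusion of the study by the PI". This covers PUSH and PWAT. Patients enter NRS pain and Wound-QoL themselves in the online survey.

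On how unblinding can arise, Section 1.3 (Risks) says "Patients will be instructed to contact the clinic in the event that dressing changes are too painful" and singles out wet-to-dry as the dressing where such pain is most to be expected. Section 7 accepts that contacting the clinic may compromise the PI's blinding.

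The pain sample size in Statistical Considerations assumes that the non-stick dressing will "reduce pain ratings by 1.3 points at the two-week checkup".

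**The concern.** The rule does not match what the blinding protects. Since patients are never blinded, the only blind that can be broken in practice is the PI's. A PI who knows the dressing might score a wound photograph differently, but cannot alter a pain or quality-of-life rating that the patient gave while already knowing the dressing. Yet the rule removes those ratings too. Read literally, an unblinding after week 2 also removes the two-week NRS already given, which is the visit behind the pain sample size.

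The exclusion comes after randomisation and may be related to outcome. The documents describe a chain from painful dressing changes, to clinic contact, to possible unblinding, to removal of data. The first link is expected more often in one arm, and pain with dressing changes is itself a primary endpoint. If removals are outcome-related and unequal between arms, both the pain comparison and the PUSH non-inferiority comparison shift.

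**Working it through.** **What the rule protects, by endpoint**

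- NRS and Wound-QoL: the rater is the patient, who is unblinded from the start. Excluding the patient because the PI is unblinded gives no protection.
- PUSH and PWAT: the rater is the PI, so the concern is real. It is already reduced in part by depersonalised photographs.

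**The plan's own figure.** "We calculate we will need 28 patients per arm to achieve 80% power". The inputs are a difference of 1.3 and an SD of 1.4, so 1.3/1.4 = 0.93 SD. The alpha for the pain test is not stated. For a two-sample t-test at 80% power, n per arm is 19.2 at two-sided 0.05, 23.3 at 0.025 and 27.4 at 0.0125. Only 0.0125 rounds up to 28, so that value is inferred and used below. Adding 2 gives 30 per arm, and 60/0.8 = 75 against the planned 74.

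**Illustration, by assumption only.** The documents give no unblinding counts. Assume 37 per arm (74/2, before dropout), normal scores, 3 patients excluded in one arm and 1 in the other, and exclusion correlated ρ = 0.3 to 0.7 with worse outcome.

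1. If the k patients with the highest tendency to be excluded are removed from 37, the mean tendency of those kept falls by 0.157 SD for k = 3 and 0.0595 SD for k = 1. The difference is about 0.098 SD.
2. The outcome shift is 0.098 × ρ, or 0.029 to 0.068 SD. Multiplied by 1.4, this is 0.041 to 0.096 points.
3. Pain, wet-to-dry loses 3: 1.30 − 0.041 = 1.26, down to 1.30 − 0.096 = 1.20. Simulated power is about 88% to 87%, against 90% if the same numbers were lost at random and 92% with no loss. At alpha 0.025 it is 93% to 92% against 94%. At 0.05 it is 96% to 95% against 97%.
4. Pain, non-stick loses 3: the difference reads 1.34 to 1.40.
5. PUSH, taking 0.84 SD as the margin (the plan fixes none) and a one-sided 98.75% bound, with a true deficit of 0.84 SD: false non-inferiority is 1.25% with no exclusion. If non-stick loses 3, it is about 1.8% to 3.0%. If wet-to-dry loses 3, it is about 0.9% to 0.7%.
6. Equal losses (3 and 3) with the same dependence on outcome: no mean shift.

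**Effect of dropout on the base.** With the plan's 20% dropout, 74 × 0.8 = 59.2, or 29.6 per arm. Pain power with no exclusion is then about 84%, not 92%. The power figures above are therefore best read as differences from random loss, not as forecasts.

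**Cost of keeping patients who change dressing.** Assume the worst case: 3 of 37 wet-to-dry patients change before scoring and take the full effect of the other dressing. Pain becomes 1.30 × 34/37 = 1.19, a loss of 0.105 points, slightly more than the largest exclusion shift in step 2. False non-inferiority for PUSH becomes about 2%, against 1.25% nominal.

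**The case against.** The strongest case on the other side is that the effect is small and that simply reversing the rule has its own cost. Most of this stands.

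- **Few events.** Section 3.3 schedules no in-person visits, and Sections 2.1 and 7 offer the research fellow as an alternative contact. Unblindings may be rare.
- **Direction.** The only arm-specific route in the documents removes high-pain wet-to-dry patients, which works against the investigators' own pain hypothesis. If those patients also heal worse, it works against non-inferiority as well.
- **Changes of dressing.** Sections 6 and 1.3 allow these patients to change or opt out. It is tempting to say that NRS and Wound-QoL can be kept at no cost. They cannot, because a later rating may refer to another dressing. This shapes the fix.

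One defence does not stand. The rule could be read as barring only data collected after unblinding. The text sets no such limit, and that reading would still drop data for reasons that can be related to outcome.

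Two stronger readings are also not supported:

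- A reader might add the non-return rule in Section 8 and the withdrawal rule in Section 6 and infer a much larger loss of data. The Section 8 sentence just before the non-return rule fills missed time points from the previous value. A patient who misses one time point is therefore kept, and the exclusion is naturally read as covering those who return nothing. The withdrawal rule does not say that data already collected are discarded.
- A reader might infer that the rule favours the non-stick dressing. That would need more poorly healing non-stick patients to be unblinded. This is possible, but nothing in the documents predicts it.

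**Conclusion.** The point holds for the unblinding rule itself. For NRS and Wound-QoL the rule is unsound at any rate of unblinding, because it removes valid data without protecting against any bias. For PUSH and PWAT it answers a real concern, but by an exclusion that can be related to outcome and arm.

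The size is not known. Under the assumed 3-versus-1 loss, pain shifts by at most about 0.10 points on 1.3, and power falls by 2 to 3 percentage points beyond random loss. False non-inferiority could reach about 3.0% if non-stick loses more. All of this rests on assumed counts, an assumed correlation, an inferred alpha and 0.84 SD taken as a margin. Confidence is high that the rule is unsound for the patient-reported endpoints, but not in any effect size or direction. It belongs at the low end of should-fix.

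**What to change.** Replace the exclusion in Section 6 with the following:

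1. A primary analysis of all randomised patients in their assigned arm, using every survey and photograph collected, including NRS and Wound-QoL of unblinded patients.
2. For PUSH and PWAT, a sensitivity analysis without the patients for whom the PI was unblinded. Because scoring takes place at study end, this leaves out all of their scores.
3. A record of any change of dressing and its date, with a required companion analysis that leaves out data after the change. Report it beside the assigned-arm result, above all for PUSH non-inferiority.
4. Unblindings, dressing changes and withdrawals reported by arm and reason.

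The cost is wording and modest analysis, with no extra patients or visits. There are four downsides:

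- Some retained PUSH and PWAT scores may come from an unblinded rater. With 3 and 1 such patients of 37 and an assumed 0.5 SD rater shift in opposite directions, PUSH moves 0.5 × 3/37 + 0.5 × 1/37 = 0.054 SD, which is why item 2 is needed.
- Retained patients who changed dressing dilute the contrast, which is why item 3 is required and not optional.
- Patients already told that their data would not be used need IRB and consent clearance before inclusion.
- The synopsis dates end in October 2023, the document is dated August 2024, and Section 2.3 reports 74 enrolled. If the change follows data collection, it must be labelled post hoc.
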